### Safety Population

The safety population will include all patients who are randomized and receive at least 1 dose of study drug and will be used for all safety analyses based on the treatment received. The Safety and ITT Populations are the same, as there were no subjects that did not receive the treatment to which they were randomized.

## 2.3 CONVENTIONS FOR DATA HANDLING

### Baseline

Baseline for a particular variable will be defined as the last available assessment for that variable prior to the initiation of first dose of study drug.

### Study Day

Study Day will be calculated from the reference start date and will be used to show start/stop day of assessments and events.

Reference start date (Study Day 1) is defined as the day of first dose for efficacy and safety analysis.  
Note: A few patients were randomized but not treated until the next day.

For assessments or events after the reference start date

Study day = date of assessment or event – reference start date + 1

For assessments or events prior to the reference start date

Study day = date of assessment or event – reference start date

## Analysis Visit

Visit-based data summaries will be presented by analysis visits. A window assessment will be performed according to the below table for any subject that missed a planned visit (on both efficacy and safety endpoints). The purpose of using this analysis window is to include potential unscheduled visits when a subject missed the planned visit. If a subject's planned visit assessment is out of the defined visit window and there is no unscheduled assessment within the same window, then this CRF collected planned visit assessment will be used for the analysis.

Period	Analysis Visit	Protocol Defined Window	Scheduled Study Day	Windows
Screening	Visit 1 (Screening)	-6 Weeks to Day -1	-41 to -1	<= -1
Treatment	Visit 2/ Randomization (Day 1)	Day 1	1	1
	Visit 3 (Week 4)	Week 4 ( $\pm 3$ days)	28	2, 42
	Visit 4 (Week 8)	Week 8 ( $\pm 3$ days)	56	43, 70
	Visit 5 (Week 12)	Week 12 ( $\pm 3$ days)	84	71, 98
	Visit 6/EOT (Week 16)	Week 16 ( $\pm 3$ days)	112	99, 119
Follow-up	Visit 7 (Follow-up)	Week 18 ( $\pm 3$ days)	126	$\geq 120$

If multiple records in the same analysis visit, the scheduled visit is preferred to the unscheduled visits, otherwise the one closest to the scheduled visit study day will be selected for the analysis and summaries. The later one is preferred if there are more than one record have the same distance to the scheduled study day.

In the derivation of post baseline extreme values (e.g., minimum, maximum, worst, last), all post baseline assessments will be included.

All data including additional unscheduled visits required for patients who need direct site assistance (due to AE monitoring, in order to fulfill screening requirements, and/or for safety maintenance) will be presented in subject listings unless otherwise specified.

## Missing and Partial Date

No imputations will be done for study visit dates, birth dates, informed consent date, and assessment dates.

Partial concomitant medication, and AE start dates will be imputed as following:

- If missing day, use the later of (01 of the month, the first dose date) if the first dose is at the same year and month of AE/CM, otherwise use the 01 of the month.
- If missing day and month, use the later of (01JAN of the year, first dose date) if the first dose year is at the same year of AE/CM, otherwise use the 01JAN of the year.
- If completely missing, no imputation will be applied

Partial concomitant medication and AE end dates will be imputed as the following:

- If missing day, use the last day of the month
- If missing day and month, use 31st December
- If completely missing, no imputation will be applied

Partial initial diagnostic dates will be imputed as: if day and/or month are missing use 01 and/or Jan. If year is missing, then no imputation, treat the date as missing. Any other imputation will be based on evidence from additional data, and will be noted for each case, should it occur.

## **2.4 CHANGES TO THE STATISTICAL ANALYSIS FROM THE PROTOCOL**

Fibrosis and inflammation markers (FIB-4, APRI, and NALFD fibrosis score (NFS)) have been added as exploratory endpoints. Additional analyses may include analyses of subjects stratifying by baseline Fib-4 at 1.3. Pro-C3 results, indicating fibrosis, may also be available for analysis.

Physical examination (including general appearance, eyes, nose, throat, head/neck/thyroid, lymph nodes, cardiovascular, lungs/chest, abdomen, genitourinary, extremities, skin, musculoskeletal, neurologic, and other) as listed in protocol section 10.2.4 are not collected.

## **2.5 IMPACT OF COVID-19 ON THE CLINICAL TRIAL**

During the data review meeting in which major protocol violations are identified, violations of the protocol that were the result of the COVID-19 pandemic will be noted.

# **3 STATISTICAL ANALYSES**

## **3.1 SUBJECT INFORMATION**

### **Disposition of Subjects**

The number and percentage of subjects for the following will be summarized by randomized treatment group and overall where applicable:

- Patients enrolled (who signed the informed consent)
- Patients included in each analysis set

- Patients completed the study
- Patients discontinued treatment early (including EOT reason)
- Patients discontinued study early (including EOS reason)

The disposition listing will include information such as: included in an analysis set, first dose date, end of treatment (EOT) status, end of study (EOS) status, and with EOT/EOS reasons.

Subjects that were screen failures and the reason for screen fail will be provided in a listing.

Per Version 3.0 of the protocol, subjects that are screen failures, may be rescreened if approved by the Medical Monitor. Subjects that have been rescreened will be noted.

### **Protocol Deviations and Violation of Inclusion/Exclusion Criteria**

All personnel involved with the analysis of the study will remain blinded until database lock for the double-blind treatment period and until major protocol violations have been identified.

Subjects who received study drug but violated any inclusion or exclusion criteria will be listed.

Protocol deviations will be captured for each site and reviewed by the medical monitor to identify major protocol deviations from the list. If noted stated elsewhere, a major protocol violation is a deviation that has an impact on patient safety, may substantially alter risks to patients, may have an effect on the integrity of the study data, or may affect the patient's willingness to participate in the study.

All major protocol deviations will be presented in a listing.

### **Demographics and Baseline Characteristics**

Descriptive summaries of demographics and other baseline characteristics will be presented by treatment group and overall using the Safety/ITT population. These summaries will include age, gender, childbearing potential, race, ethnicity, height, weight and body mass index (BMI).

Conversion factors and calculations for height and weight are:

- Height (in cm) = height (in inches) \* 2.54
- Weight (in kg) = weight (in lbs) \* 0.4536

By subject listings for demography and baseline characteristics will be provided.

### **Medical and Surgical History**

NASH/NAFLD history variables characteristics will be summarized by randomized treatment group and total on ITT.

Medical histories include type of disease under study (NASH or NAFLD), duration of disease under study, NASH confirmed by live biopsy (Yes or No), and whether patients have any other relevant medical or surgical history. The duration of disease under study is calculated as (the date of randomization – date of initial diagnosis + 1)/365.25. Imputed date of initial diagnosis date will be used if the collected date is partial.

If applicable, the other relevant medical and surgical history will be coded by latest MedDRA version. The number (percent) of subjects reporting a history of any other relevant medical or surgical history, will be summarized for each randomized treatment group and overall.

A subject data listing of medical and surgical history will be provided.

### **Prior and Concomitant Medications**

All medications with a stop date prior to and within 3 months (92 days) of the date of first dose are regarded as prior medication. All medications with a start date or stop date on or after the first dose date are regarded as concomitant medication. Medications where start date and end date are both completely missing (both dates cannot be imputed) will be treated as concomitant medications.

The number (percent) of subjects who took prior and concomitant medications will be summarized respectively by Anatomic Therapeutic Chemical (ATC) level and preferred term for each randomized treatment group and overall on ITT. Subjects taking the same medication multiple times will only be counted once for that ATC class and preferred term. A subject level listing will also be presented.

All investigator terms for medications recorded on the CRF will be coded using the World Health Organization (WHO) Drug Dictionary B3, March 2019 version.

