  - b. Ursodeoxycholic acid, thiazolidinediones, or obeticholic acid within 3 months prior to Screening
  - c. Statins and other lipid-modifying therapies must have been stable for  $\geq 3$  months prior to Screening
  - d. Oral antidiabetic drugs (other than those specifically excluded) must have been stable for  $\geq 3$  months prior to Screening

- e. Agents (including herbal over-the-counter weight-loss preparations) or medications known to significantly impact body weight within 3 months prior to Screening (e.g., sibutramine, phenetamine, and orlistat)
- 11. History of significant alcohol consumption, defined as an average of >20 g/day in female patients and >30 g/day in male patients, for a period of >3 consecutive months within 1 year prior to Screening, hazardous alcohol use (Alcohol Use Disorders Identification Test score ≥8), or an inability to reliably quantify alcohol consumption based upon judgment of the Investigator
- 12. Weight change ≥10% within the 6 months prior to Screening or ≥5% within the 3 months prior to Screening
- 13. Prior or planned (during the study period) bariatric surgery (e.g., gastroplasty, sleeve gastrectomy and roux-en-Y gastric bypass)
- 14. Type 1 diabetes by medical history
- 15. Uncontrolled Type 2 diabetes defined as hemoglobin A1c (HbA1c) >9.5% at Screening (patients with HbA1c >9.5% may be rescreened) or requiring oral diabetes medication dose adjustment >10% within 2 months prior to Screening
- 16. Clinical hyperthyroidism or hypothyroidism or screening hormone results pointing to thyroid dysfunction. Patients receiving dose-stable thyroid replacement therapy for ≥3 months prior to Screening will be allowed to participate as long as thyroid tests (thyroid-stimulating hormone/triiodothyronine/thyroxine) show that the patient is euthyroid
- 17. History of any condition causing malabsorption such as chronic pancreatitis, extensive bowel/small intestine surgery, celiac disease, or bile flow obstruction
- 18. History of any condition associated with acute or chronic diarrhea such as inflammatory bowel disease (IBD), functional diarrhea, irritable bowel syndrome (IBS) with predominant diarrhea, IBS with mixed bowel habits, or unclassified IBS
- 19. History of ischemic colitis

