### **8.7 Concomitant Therapy and Prohibited Medications**

The Investigator will note all ongoing medication and any medication recently stopped (within 3 months prior to Visit 2) in the eCRF. At Visits 2 through 6, all changes in medication (stopping or starting new medication or changes in dose) will be recorded in the eCRF.

All medications taken by a patient within 3 months prior to the first intake of study drug are regarded as prior medication.

All medications taken by a patient on or after the first intake of study drug, and which continue to be taken during the study, are regarded as concomitant medication.

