## Safety Endpoints

The safety endpoints for this study include clinical laboratory assessments, vital signs, AEs, ECGs, and concomitant medications.

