## Exploratory Efficacy Endpoints

The test results and change from baseline (unless otherwise specified) to week 4, week 8, week 12, week 16, and follow-up, will be summarized for the following variables:

- Fasting glucose, insulin, homeostatic model assessment-insulin resistance, HbA1c, free fatty acids
- GLP-1, FGF-19, and C4 levels
- High-sensitivity CRP
- Lanosterol and beta-sitosterol
- Body weight, BMI, waist circumference, and waist-to-hip ratio (Physical examination)
- Apolipoprotein A1 and Apolipoprotein B
- Fibrosis and inflammation markers: FIB-4, APRI and NFS

By patient figures (spaghetti plots) plots for the absolute value and change from baseline over time will be provided for each efficacy endpoint. An MMRM of change from baseline will be provided for all efficacy endpoints. Two plots for each MMRM analysis will be provided, one figure by treatment arm, and a second figure for the contrast between treatment arms. Correlation matrices will be provided for efficacy endpoints overall, by treatment, and by treatment by study visit.

$$\text{FIB-4} = [\text{Age (years)} \times \text{AST (U/l)}] / [\text{Platelet}(\times 10^9/l) \times (\text{ALT(U/l)})^{0.5}]$$

$$\text{APRI} = [\text{AST (IU/l)} / \text{AST (ULN)}] / \text{Platelet}(\times 10^9/l) \times 100$$

$$\begin{aligned} \text{NAFLD fibrosis score} = & -1.675 + 0.037 \times \text{age (years)} + 0.094 \times \text{BMI (kg/m}^2\text{)} + 1.13 \times \\ & \text{IFG/diabetes (yes} = 1, \text{no} = 0\text{)} + 0.99 \times \text{AST/ALT ratio} - 0.013 \times \text{platelet}(\times 10^9/l) - 0.66 \times \\ & \text{albumin (g/dl)} \end{aligned}$$

Additional analyses may be performed to identify differences in treatment effect by baseline characteristics, such as dichotomized subjects by FIB-4 <1.3, and  $\geq 1.3$ , BMI ( $<30/\geq 30$ ), type 2 diabetes (Y/N), cardiovascular co-morbidities (Y/N), lipid lowering concomitant medications (Y/N), and LDL-C (by  $</\geq$  median value).

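### Read literally, the SAP's date rules make a drug with a known start before the first dose that is still ongoing neither prior nor concomitant, although the protocol counts it as both

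*SAP*

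**What the plan says.** SAP 3.1, under Prior and Concomitant Medications, sets three rules.

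- Prior: "All medications with a stop date prior to and within 3 months (92 days) of the date of first dose".
- Concomitant: "All medications with a start date or stop date on or after the first dose date are regarded as concomitant medication".
- Fallback: "Medications where start date and end date are both completely missing (both dates cannot be imputed) will be treated as concomitant medications".

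For an end date with no part recorded, SAP 2.3 (Missing and Partial Date) says: "If completely missing, no imputation will be applied". The SAP has no rule for a drug marked as ongoing.

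Protocol 8.7 uses intake instead of dates. Anything taken in the 3 months before first intake is prior. The concomitant class is "All medications taken by a patient on or after the first intake of study drug, and which continue to be taken during the study". A background drug taken before and after Day 1 belongs to both. SAP 2.4, which lists changes from the protocol, does not mention a change here.

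SAP 1.2 names the safety endpoints as "clinical laboratory assessments, vital signs, AEs, ECGs, and concomitant medications". Protocol 11.2.2.7 promises a summary of concomitant drug use over the treatment period, and protocol 11.2.2.3 promises one of prior medication.

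**The concern.** The drugs that fall through are the ones a reader most wants to see. Protocol 7.2.2, criterion 10c, says "Statins and other lipid-modifying therapies must have been stable for" at least 3 months before Screening, and 10d says the same of oral antidiabetics. Permitted therapy in these classes therefore normally started well before Day 1 and, if uninterrupted, has no stop date.

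The primary endpoint is LDL-C. The list of baseline characteristics in SAP 3.1 does not include background medication, so the prior and concomitant tables are where one would check whether lipid-lowering and antidiabetic therapy was balanced between two arms of 23. Under the literal rules, the concomitant table would show mainly drugs started or stopped on study, and the prior table only drugs stopped shortly before it.

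**Working it through.** No figure in the plan needs reproducing. The check applies the SAP's rules to patterns of start and stop dates and sets the result beside protocol 8.7. The first dose date of 15 November 2019 is illustrative, so the 92-day window opens on 15 August 2019.

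Rules as coded:

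- Prior = a stop date exists, and 15 August 2019 ≤ stop < 15 November 2019.
- Concomitant = start ≥ 15 November 2019, or stop ≥ 15 November 2019, or both dates completely missing.
- Partial start dates are imputed first, under SAP 2.3. A start known only to the year is moved to the first dose date if that year is the first-dose year. A start known to the month is moved there if year and month both match. Otherwise the first day of the year or month is used.
- A completely missing stop date stays missing.

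| Start | Stop | SAP prior | SAP concomitant | Protocol 8.7 (prior, concomitant) |
|---|---|---|---|---|
| 10 Mar 2018 | ongoing | no | no | yes, yes |
| 2016 (year only) | ongoing | no | no | yes, yes |
| May 2019 (no day) | ongoing | no | no | yes, yes |
| 2019 (year only) | ongoing | no | yes | prior depends on true start; yes |
| Nov 2019 (no day) | ongoing | no | yes | prior depends on true start; yes |
| completely missing | ongoing | no | yes | prior depends on true start; yes |
| 10 Mar 2018 | 5 Jan 2020 | no | yes | yes, yes |
| 10 Mar 2018 | 20 Oct 2019 | yes | no | yes, no |
| 1 Dec 2019 | ongoing | no | yes | no, yes |
| 10 Mar 2018 | 1 Jul 2019 | no | no | no, no |

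The first three rows are the gap: an earlier start that is not imputed to the first dose date, and no stop date. The seventh row shows a second mismatch: a background drug stopped on treatment is concomitant in both documents, but prior only in the protocol.

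Rows four to six show that some ongoing drugs are caught. The November 2019 row cannot be a therapy begun at least 3 months before Screening. The year-only and completely missing starts could be, but they are caught because the date is incomplete; a site that records the date fully loses the drug from the tables.

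On scale, the documents give no rate of background statin use. Assuming 30% to 60% of 46 patients, 0.30 × 46 = 13.8 and 0.60 × 46 = 27.6, so up to 14 to 28 patients would be absent from the statin rows. The true count would be lower by those whose start date is incomplete in the ways above, or who stop on or after the first dose.

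**The case against.** The best defence is that no programmer would do this. The SAP is written to protocol version 3.0, which defines the classes by intake. SAP 2.4 declares no departure, which fits loose wording as well as deliberate narrowing. The fallback resolves doubt toward concomitant. An ongoing drug has no end date yet, which is not plainly the same as a missing one, and a programmer may read ongoing status as a stop after the first dose. The eCRF is not among the documents, so its coding of ongoing drugs is unknown. All of this makes a sensible outcome likely. It does not make it the specified one: the SAP deals expressly with absent dates and extends concomitant status only where both are absent.

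The second defence is that the consequence is descriptive. That stands. SAP 3.1 also provides a subject-level listing that is not limited to classified drugs, and SAP 3.4 plans no inferential safety statistics. SAP 3.4 also leaves concomitant medication out of its own list of safety variables, but SAP 1.2 and protocol 11.2.2.1.2 both name it as a safety endpoint.

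Three stronger readings are tempting and go beyond the documents.

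- A reader might infer that every ongoing background drug is lost. Rows four to six of the table show otherwise.
- A reader might infer that the subgroup "lipid lowering concomitant medications (Y/N") would code continuing statin users as non-users. SAP 3.2 introduces that subgroup among baseline characteristics, makes the analysis optional, and does not say it is derived from the SAP 3.1 classes.
- A reader might infer that the lipid-lowering covariate in the primary model is miscoded. It is a separately named baseline variable with no stated derivation, so miscoding is possible but not shown.

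**Conclusion.** The concern holds for the summary tables. Followed as written, SAP 3.1 gives prior and concomitant tables that contradict protocol 8.7 and do not deliver the summaries promised in protocol 11.2.2.3 and 11.2.2.7. It is a stated rule with a wrong result for a named safety endpoint, not merely a missing detail.

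This rests on two assumptions: that an ongoing drug carries no stop date in the data, and that the rules are programmed literally. The size in patients cannot be fixed from the documents; the range shown depends on an assumed statin rate and applies to the tables only, not to the subgroup or the covariate.

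**What to change.** - Concomitant, SAP 3.1: keep the present limbs and add drugs that started before the first dose and are recorded as ongoing at the first dose date. The first three rows of the table then become concomitant; no other row changes.
- Prior, SAP 3.1: adopt the intake basis of protocol 8.7, so that any drug taken in the 3 months before first dose is prior, including those that continue. State in a footnote that a drug may appear in both tables.
- Lipid-lowering flags, SAP 3.2: state that the baseline covariate and the subgroup are based on drugs in use on the first dose date.

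A blanket rule that treats every missing end date as ongoing would not be a good substitute. Protocol 8.7 contains no such rule, and it would turn a drug stopped before Day 1 with an unknown stop date into a concomitant one. The trigger should be recorded ongoing status.

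The cost is a few sentences and a derivation rule. No new data should be needed, since protocol 8.7 already requires ongoing medication to be noted in the eCRF; how that status is stored should be confirmed before programming.

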## **3.2 EFFICACY ANALYSES**

### **Primary Endpoint**

The primary efficacy endpoint for this study is the change from baseline in serum LDL-C at week 16.

Change from baseline in serum LDL-C will be analyzed by using an analysis of covariance (ANCOVA) after the missing data imputation. The ANCOVA model will include treatment group as a factor, baseline LDL-C and baseline LDL-C by treatment interaction values, and baseline **lipid lowering medications (Yes or No)** as covariates.

Serum LDL-C results and the change from baseline at each scheduled time point, along with the minimum and maximum post baseline value, will be summarized using descriptive statistics.

Box plots for serum LDL-C results absolute value and change from baseline overtime will be provided.

- **Step 2:** After the intermediate missing values have been imputed, subjects are categorized to 3 groups: 1) Completers (defined as subjects who completed the study treatment) in the control arm with non-missing value at week 16. 2) Subjects with a missing value at week 16 in both arms. Missing values in these subjects will be imputed using subjects in group 1. 3) Completers in the active arm with non-missing value at week 16 (based on the analysis visit window in section 2.3). These subjects will not be used to impute missing values in the next step.
- **Step 3:** At this point, each subject in the 200 data sets generated at step 1 either has complete data or has monotone missing data. Subjects in group 1 in Step 2 will be used to impute missing values in subjects in group 2. Missing data in group 2 will be imputed as the predicted value from a regression model with treatment arm, LDL-C baseline, baseline **lipid lowering medications**, and the change from baseline of all previous scheduled visits included in the model. Since the dataset has a monotone missing data pattern, the imputation process will start from the earliest visit with missing data (e.g. week 4) through week 16 in a sequential order. SAS Proc MI with option Monotone Reg, n impute=1, and seed = 25380 will be applied. The imputation will be done for each one of the 200 data sets generated at step 1.
- **Step 4:** After imputation for monotone missing values at Step 3, subjects in all 3 groups will be pooled and sorted by imputation sequence (variable name \_Imputation\_ from Step 1).
- **Step 5:** Each imputed complete dataset will be analyzed using the analysis of covariance (ANCOVA) model with the randomized treatment group as a factor and baseline LDL-C values

as a covariate. The estimates of least-square means (lsmeans), least-square mean differences 95% CI, and p-value will be generated for each one of the 200 imputed complete datasets.

- **Step 6:** The results from the 200 complete datasets, including lsmeans and lsmean difference with their corresponding 95% confidence intervals, and the p-value between elobixibat 5 mg and placebo will be combined using SAS® procedure PROC MIANALYZE for statistical inference.

The above primary efficacy analysis will be repeated using the PP population.

